As part of the blind analysis review, we will ascertain whether or not study outcomes differ for rural and urban sites. If they do not differ, as anticipated, we will combine the data from the five sites in Karachi with the five sites in Thatta. If differences are detected via descriptive analyses, we will present stratified results, but will be unable to test for significant differences as the trial was not powered for that purpose. In that event, the focus will be on the urban sites only, whose sample size (n=342) was powered to test the non-inferiority hypothesis.

Other comparisons between groups will be primarily descriptive to explore the differences in the provision of DMPA services and client satisfaction measures by each cadre of provider, by DMPA type and urban/rural setting if those data are not pooled. Similarly, objective and provider-perceived comparisons between injection techniques and injection characteristics, respectively, will be primarily descriptive and exploratory.

Analyses by Objective

Objective 1: *To assess whether LHWs can screen and initiate women on DMPA injections as safely and effectively as LHV.*

To answer this objective, the analysis will report the odds ratio of appropriate screening and counseling by LHWs compared with LHV using multi-level generalized mixed models as described above. The generalized linear mixed model accounts for the multilevel structure of the data (i.e., clinics and providers).

Objective 2: *Assess whether DMPA clients of Lady Health Workers and Lady Health Visitors are equally satisfied with their respective providers and the family planning services they provide.*

Descriptive analysis will be completed using indicators of client satisfaction and client-provider interactions for LHW and LHV clients.

Table 2: Summary of analysis approach and data sources for the primary and secondary outcomes

Outcome	Analysis	Stratified by	Source
Objective 1 Outcomes			
Screening for DMPA use	GLMM and descriptive	Cadre, urban/rural	Observation checklist of screening and gold-standard nurse's assessment
Counseling/Discussion of DMPA side effects, danger/warning signs, advantages and disadvantages	GLMM and descriptive	Cadre, urban/rural	Observation checklist of screening
Appropriate injection technique*	Descriptive	Cadre, urban/rural	Observation checklist for DMPA-IM, q1-q17; Observation checklist for DMPA-SP, q1-q22
Needle stick injuries*	Descriptive	Cadre, urban/rural	LHW/LHV questionnaire
Use of client (re)injection log*	Descriptive	urban/rural	LHW/LHV questionnaire, qLHW6
Objective 2 Outcomes			
Client satisfaction with DMPA*	Descriptive	Cadre, DMPA type	Client exit interview, q313
Client satisfaction with service delivery*	Descriptive	Cadre, DMPA type	Client exit interview, q318
Client comfort asking provider questions*	Descriptive	Cadre, DMPA type	Client exit interview, q303
Friendly and respectful behavior by provider*	Descriptive	Cadre, DMPA type	Client exit interview, q301

* If the data are pooled, there will be no urban/rural stratification

Objective 1 Table Shells: Screening and counseling for DMPA

Table 1: Odds of appropriate screening and counseling for DMPA initiation by Lady Health Workers compared with Lady Health Visitors in Pakistan

OR	90%CI	p-value
Appropriate screening		
Appropriate counseling		

Appropriate screening defined as agreement between the provider and independent assessment by a gold standard nurse
Appropriate counseling defined as having discussed side effects, warning/danger signs, advantages, and disadvantages of DMPA

95% CI and p-value reported for test of non-inferiority

Table 2: Exploratory analysis of factors affecting appropriate screening for DMPA initiation by Lady Health Workers compared with Lady Health Visitors in Pakistan

	N (%)	OR (or β)	95%CI	p-value
Age				
Age cat 1				
Age cat 2				
Etc.				
Marital status				
Marital status 1				
Marital status 2				
Etc.				
Education level				
Education level 1				
Education level 2				
Etc.				
Years of service				
Categorical or continuous TBD				
Years of DMPA experience				
Categorical or continuous TBD				
Avg. DMPA injections/month				
Categorical or continuous TBD				

Appropriate screening defined as agreement between the provider and independent assessment by a gold standard nurse

Table 3: Exploratory analysis of factors affecting appropriate counseling for DMPA initiation by Lady Health Workers compared with Lady Health Visitors in Pakistan

	N (%)	OR (or β)	95%CI	p-value
Age				
Age cat 1				
Age cat 2				
Etc.				
Marital status				
Marital status 1				
Marital status 2				
Etc.				
Education level				
Education level 1				
Education level 2				
Etc.				
Years of service				
Categorical or continuous TBD				
Years of DMPA experience				
Categorical or continuous TBD				
Avg. DMPA injections/month				
Categorical or continuous TBD				
Appropriate counseling defined as having discussed side effects, warning/danger signs, advantages, and disadvantages of DMPA				

Table 4: Comparison of Lady Health Workers and Lady Health Visitors on DMPA service delivery indicators (n, %)

	Urban	Rural		
	LHW	LHV	LHW	LHV
Appropriate screening				
Appropriate counseling				
side effects				
danger signs				
advantages/disadvantages				
Appropriate injection technique				
Needle stick injuries				
Client log maintained				

Objective 2: Client Satisfaction and Client-Provider Interaction

Table 5: Exemplar of Client Satisfaction and Client-Provider Interaction items (n, %)

	LHW		LHV	
	SP	IM	SP	IM
Satisfaction with method				
very satisfied				
somewhat satisfied				
not satisfied				
Satisfaction with services				
very satisfied				
somewhat satisfied				
not satisfied				
Satisfaction with provider				
very satisfied				
somewhat satisfied				
not satisfied				
Comfort asking questions				
yes				
no				

Figure 1: Graphic presentation of observation checklist for screening

Observation Checklist to Evaluate Providers Who Screen Clients for Initial DMPA Use

Type of provider being observed: Lady Health Worker
Lady Health Visitor

Please record the response given to the provider by the client for the following items. If the provider does not ask the question, please draw a line through the item.

NO	1. Have you ever been told you have breast cancer?	YES
NO	2. Have you ever had a stroke or heart attack, or do you currently have a blood clot in your legs or lungs?	YES
NO	3. Do you have a serious liver disease or jaundice (yellow skin or eyes)?	YES
NO	4. Have you ever been told you have diabetes (high sugar in your blood)?	YES
NO	5. Have you ever been told you have high blood pressure?	YES
NO	6. Do you have bleeding between menstrual periods, which is unusual for you, or bleeding after intercourse (sex)?	YES
NO	7. Have you ever been told that you have a rheumatic disease such as lupus?	YES
NO	8. Do you have two or more conditions that could increase your chances of a heart attack or stroke, such as smoking, obesity, high blood pressure, or diabetes?	YES
NO	9. Are you currently breastfeeding a baby less than 6 weeks old?	YES

If the client answered NO to *all of questions 1–9*, did the provider tell her she is a good candidate for DMPA?
Yes No
Did provider proceed to questions 10–15?
Yes No

If the client answered YES to *question 1*, did the provider tell her that she is not a good candidate for DMPA? Yes No

Did the provider counsel her about other available methods or refer? Yes No

If the client answered YES to *any of questions 2–8*, did the provider tell her that DMPA cannot be initiated without further evaluation. Yes No
Did the provider then evaluate or refer her as appropriate? Yes No
Did the provider give her condoms to use in the meantime? Yes No

If the client answered YES to *question 9*, did the provider instruct her to return for DMPA as soon as possible after the baby is six weeks old?

Yes No

Please record the response given to the provider by the client to the items below. If the provider does not ask the question, please draw a line through that item.

YES	10. Did your last menstrual period start within the past 7 days?	NO
YES	11. Have you abstained from sexual intercourse since your last menstrual period or delivery?	NO
YES	12. Have you been using a reliable contraceptive method consistently and correctly since your last menstrual period or delivery?	NO
YES	13. Have you had a baby in the last 4 weeks?	NO
YES	14. Did you have a baby less than 6 months ago, are you fully or nearly-fully breastfeeding, and have you had no menstrual period since then?	NO
YES	15. Have you had a miscarriage or abortion in the last 7 days?	NO

Please record the action taken by the provider on the back of this sheet.

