## **II. Objectives and Outcomes**

The overall goal of the trial is to provide high-level evidence that lay or community health workers can safely and effectively screen and initiate women who choose to use injectable contraceptives. The primary objective is:

To assess whether the community health worker cadre, Lady Health Workers (LHWs) in Pakistan can screen and initiate women on intramuscular and subcutaneous Depo Provera injections as safely and effectively as their clinically-trained counterparts, Lady Health Visitors (LHVs).

Although LHWs are already allowed to provide follow-up doses in the community, this RCT will focus on the comparison of safety and effectiveness of screening, counseling and first-time administration of DMPA IM and SP. Rather than focusing on determining whether services are better provided by one of the two health worker cadres, we want to determine if LHWs can perform just as well as the more experienced LHVs. Therefore, the trial will be powered specifically to detect non-inferiority (i.e., no difference) within a tolerance margin in the performance of LHWs compared to LHVs with regard to screening--the procedure that determines a woman's eligibility to receive DMPA. We consider the assessment of the screening for DMPA use as the primary outcome of interest for addressing the primary objective. However, in addition to screening, metrics for counseling and administration of DMPA will constitute the endpoints for the primary objective described below:

- Proportion of Lady Health Workers and Lady Health Visitors that appropriately screen women for DMPA use;
- Proportion of Lady Health Worker and Lady Health Visitor clients that report discussion with their respective providers on side effects, danger signs, advantages and disadvantages of DMPA use;
- Proportion of Lady Health Workers and Lady Health Visitors that demonstrate appropriate injection technique
- Proportion of Lady Health Workers and Lady Health Visitors that report needle stick injuries;
- Proportion of Lady Health Workers that properly maintains a client (re)injection log.

Details on analysis of these endpoints will be provided in a separate data analysis plan.

The secondary objective is:

To assess whether DMPA clients of Lady Health Workers and Lady Health Visitors are equally satisfied with their respective providers and the family planning services they provide.

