Ten (10) health facilities will be selected from two districts in Sindh: Karachi and Thatta. Within those districts, health facilities in urban areas of Karachi and rural areas of Thatta will be approached to participate in the trial. The health facilities will be selected based on 1) the number of DMPA acceptors; 2) availability of both LHV and LHWs; and 3) logistical factors. Table 1 provides a proposed sample of study sites with DMPA client volume from the most recent month of available data. Final selection of districts and health facilities within them will be determined in collaboration with in-country partners, AKU and Jhpiego as more information on the distribution of LHWs and LHV and client volume in Sindh becomes available. The sample, including the number of districts or the number of health facilities and their distribution may be adjusted based on this information. For example, we may add another rural district if sufficient numbers cannot be found that meet criteria for LHW experience, current status (i.e., active, not active) or the health facility's ability or willingness to participate in the trial. Alternatively, more sites may be added within the same districts if client volume or health provider interest in trial participation is low.

Table 1. Proposed health facilities and most recent DMPA client volume data

Facility name	District (location)	Client volume in most recent month available of new and continuing injectable clients*
RHS-A Center, SG Hospital Saudabad	Karachi (urban)	30
FWC, SG Hospital Korangi 5	Karachi (urban)	125
FWC-Shah Faisal Colony No. 1, KMS MCH Center	Karachi (urban)	82
FWC Korangi 33-C, BHU Korangi 33-C	Karachi (urban)	73
RHS-A Center, SG Hospital Ibrahim Hyderi	Karachi (urban)	67
RHS-A Center, DHQ Hospital Makli	Thatta (rural)	32
RSH-A Center, THQ Hospital Mirpur Sakro	Thatta (rural)	19
Rural Health Center, Jherruk	Thatta (rural)	0 
RHS-A Center, THQ Hospital Sujawal	Thatta (rural)	38
RHS-A Center, THQ Hospital Mirpur Bathoro	Thatta (rural)	16

\*Data received 2/20/2017

It is anticipated that this proposed study site will have sufficient clients during the data collection period.

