#### Randomization procedures

A randomization manager from FHI 360, who is not otherwise involved in the study, will prepare a computerized randomization list using permuted blocks before the start of the study. These envelopes

---

a A total of 342 DMPA acceptors will be distributed among the 5 health facilities in urban Karachi district. On average, about 68 acceptors will be recruited per facility of which half will be assigned to LHWs.

[figure not shown]
will be given to the local PI at AKU who will distribute the envelopes to RAs assigned to study health facilities. These RAs will open the randomization envelopes and inform LHWs or LHV when they have been selected to provide DMPA services (screening, counseling) and which form of DMPA (IM or SP) they will provide after the independent third party verifies the client's eligibility for DMPA use.

Women will be randomized in a 1:1 ratio to proceed with DMPA screening by an LHV or LHW. After the independent staff member confirms the client's eligibility to use DMPA, an identical randomization procedure will be performed to randomize women to receive either DMPA IM or SP. The master randomization list will be maintained at FHI 360 and will not be available to study staff.

Randomization groups will be concealed in sequentially numbered, sealed opaque envelopes (SNOSE). We will instruct study staff never to open an envelope until the participant has given consent to participate in the study, is found to be eligible for the study, and is present for DMPA screening and the subsequent administration of the injectable. These envelopes will be provided to AKU in advance of trial implementation. The opened randomization envelopes will be retained as source documents and will be kept under secure and restricted access to protect the confidentiality of the participants.

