This is an open-label study – neither study staff nor participants will be blinded to study treatment arms after the point of randomization. Nonetheless, strict policies will be in place to preserve randomization integrity. Randomization documentation will be stored in a secure location. Data recording, assessment of the primary and secondary study outcomes, and other assessments, such as DMPA eligibility assessment by independent facility staff, will be blinded to treatment arm where possible. The FHI 360 lead statistician and data analysts will perform a blinded review of the data to make final statistical decisions that could affect the comparison of the primary and secondary outcomes before fully unblinding the data for final analyses. Details of the analysis processes will be described in the detailed analysis plan.

Screening, counseling and DMPA administration will all be performed by the same LHW or LHV randomized to provide services to that client. The receipt of DMPA IM or SP is being randomized to avoid an imbalance of DMPA type that could occur if clients are given the choice between the two delivery systems. Similarly, provider bias/preference for one form or the other of DMPA could result in the same. The following graphic describes the procedures, including randomization, to be adopted in this trial.

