IRBNET# 1035709: A randomized controlled trial of safety and effectiveness of Depo Provera intramuscular and subcutaneous administration comparing lay Lady Health Workers with clinically-trained Lady Health Visitors in Pakistan

STATISTICAL ANALYSIS PLAN

This statistical analysis plan gives a detailed explanation of the data analysis summary included in the study protocol.

I. Study Objectives

The goal of this evaluation is to assess whether the community health worker cadre, Lady Health Workers (LHWs) in Pakistan can screen and initiate women on intramuscular (IM) and subcutaneous Depo Provera injections as safely and effectively as their clinically-trained counterparts, Lady Health Visitors (LHV). Although LHWs are already allowed to provide follow-up doses in the community, this RCT will focus on the comparison of safety and effectiveness of screening, counseling and administration of DMPA IM and the subcutaneous injection, Sayana Press® (SP).

The study's primary outcomes are:

- Proportion of Lady Health Workers and Lady Health Visitors that appropriately screen women for DMPA use;
- Proportion of Lady Health Worker and Lady Health Visitor clients that report discussion with their respective providers on side effects, danger signs, advantages and disadvantages of DMPA use;
- Proportion of Lady Health Workers and Lady Health Visitors that demonstrate appropriate injection technique
- Proportion of Lady Health Workers and Lady Health Visitors that report needle stick injuries;
- Proportion of Lady Health Workers that properly maintains a client (re)injection log.

A secondary objective is to assess whether the clients of LHWs and LHV are equally satisfied with their respective providers and the family planning services they provide.

The study's secondary outcomes are:

- Satisfaction with the method;
- Satisfaction with the services received from the provider;
- Reports of client ability to speak freely and ask questions of provider;
- Friendly and respectful behavior toward client.

II. Study Design

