We require a minimum of 342 DMPA clients randomized to receive care from either the LHV or an LHW (1:1 allocation) for 90% power and 5% significance level to test the non-inferiority hypothesis that LHWs can screen potential DMPA clients for method initiation just as adequately as LHVs with a non-inferiority margin of 7.5%, assuming that both LHVs and LHWs perform at a 95% success rate. In Pakistan, there is usually at least one LHV assigned to a health facility and many more LHWs affiliated with and under the supervision of resident LHVs. Therefore, we will use a 3 to 1 ratio of LHWs to LHVs at each health facility in the trial.

For logistical reasons, we plan to obtain the full target sample size of 342 DMPA initiators from the 5 urban health facilities in Karachi to ensure that adequate analyses can be done with this group. We will recruit additional participants (~100) from 5 rural facilities in Thatta to help assess possible differences in performance between LHV and LHWs in rural and urban areas, but the expectation is that there will be no difference. LHWs undergo standardized training in Pakistan. If we can be comfortable that providers in rural and urban areas perform in similar manner, the overall sample size for the analysis may be pooled for an increase in power. The decision whether to pool the data or not will be made during the blind review of the data as described below.

Given the relationship between LHWs and LHV within clinics, we plan to account for the correlations of participant outcomes within providers and providers within clinics in the analysis. We expect that some of these correlations would lead to decreases in power and others to lead to increases in power for within clinic comparisons. Power calculations were not adjusted for these potential correlations as the net effect on power may be offset with each other.

V. General Analytic Considerations

A. Data Sources

A.1 Client exit interview

Client exit interviews measure the study's secondary outcomes of client satisfaction with the method and provider. The exit interview also provides additional information related to appropriate screening such as discussion of side effects, warning/danger signs, advantages and disadvantages of DMPA use with clients. The client exit interview includes questions on the following domains:

1. Sociodemographic characteristics
2. Experiences using contraceptive methods
3. Factors in her decision to use DMPA

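### Needle-stick injury is compared as a share of providers, although each LHV gives about three times as many trial first doses as each LHW, and the protocol and SAP disagree on which LHWs are asked

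*SAP*

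**What the plan says.** Needle-stick injury is among the primary outcomes in the protocol (Study Summary; II. Objectives and Outcomes) and in SAP section I, worded as "Proportion of Lady Health Workers and Lady Health Visitors that report needle stick injuries". SAP Table 2 gives the analysis as descriptive, from the LHW/LHV questionnaire. The SAP Table 4 shell shows n and % by cadre. SAP section VIII describes comparisons outside the modelled outcomes as "primarily descriptive to explore the differences in the provision of DMPA services and client satisfaction measures by each cadre of provider". SAP section V.C defines screening, counseling and injection technique, but not this outcome. The questionnaire is described only by its domains.

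Three design features fix who gives the trial first doses:

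- Protocol, Randomization procedures: "Women will be randomized in a 1:1 ratio to proceed with DMPA screening by an LHV or LHW".
- SAP section IV: "Therefore, we will use a 3 to 1 ratio of LHWs to LHVs at each health facility in the trial". SAP Table 1 gives 30 LHWs and 10 LHVs.
- Protocol, Randomization procedures: "Screening, counseling and DMPA administration will all be performed by the same LHW or LHV randomized to provide services to that client".

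On who is interviewed, the protocol (Pilot testing and recruitment procedures; LHW/LHV interview) takes all LHVs but only LHWs who served at least nine new DMPA clients, lowered to four at rural sites. SAP section V.B says all participating LHWs and LHVs will be asked.

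**The concern.** A provider who gives more injections has more chances of an injury. A share of providers is therefore a fair comparison of cadres only if exposure per provider is similar. For trial first doses the design makes it unequal by a factor of three. The distortion runs in favour of LHWs, the cadre whose safety the trial is meant to establish, and this is the only comparison of injury to the provider.

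The plan does not restrict the outcome to trial first doses either. Interviews come four to six months after trial initiation, by which time the protocol expects providers to have given follow-up injections as well, and "LHWs are already allowed to provide follow-up doses in the community". With no stated window or scope, a reader cannot tell what exposure lies behind the two percentages.

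The interview conflict leaves the LHW denominator open for this outcome and for the (re)injection-log outcome, which is collected at the same interview. It would also affect a per-injection rate: under the protocol rule, low-volume LHWs are not asked, while LHV coverage is complete.

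**Working it through.** **Trial first doses per provider.** Inputs: 342 urban clients at 5 sites and about 100 rural clients at 5 sites (Sample size), 1:1 allocation, one LHV and three LHWs per site.

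- Urban: 342/5 = 68.4 clients per site, and half is 34.2 per cadre. This reproduces the protocol's own figures of about 68 and about 34. Per LHV: 171/5 = 34.2. Per LHW: 171/15 = 11.4.
- Rural: per LHV 50/5 = 10; per LHW 50/15 = 3.3.
- Overall: 221/10 = 22.1 against 221/30 = 7.4.

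The ratio is 3.0 throughout. These are upper averages, since clients found ineligible receive no injection. LHW rotation follows availability, so individual loads will vary.

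**Expected shares at equal risk.** With risk r per injection and m injections, the expected share of providers with at least one injury is 1 − (1 − r)^m. The documents give no r; the values below are assumptions.

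| r | Urban LHV | Urban LHW | Ratio |
|---|---|---|---|
| 0.1% | 3.4% | 1.1% | 2.97 |
| 0.5% | 15.8% | 5.6% | 2.84 |
| 1% | 29% | 11% | 2.69 |
| 2% | 50% | 21% | 2.43 |

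The rural ratio runs from 2.99 to 2.81. Over all sites at 1%, the shares are 19% and 7.1% (ratio 2.7). Expected injured providers are nearly equal: LHV 5(0.291) + 5(0.096) = 1.9; LHW 15(0.108) + 15(0.033) = 2.1. So the n would look balanced while the percentage, which is the defined outcome, would not.

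**Chance of no injury at all.** (1 − r)^442 is 64% at 0.1%, 11% at 0.5% and 1.2% at 1%. With no injury the distortion does not appear.

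**If other injections count.** Protocol Table 1 ("Client volume in most recent month available of new and continuing injectable clients") sums to 30 + 125 + 82 + 73 + 67 = 377 at the five urban sites in one month, against 342 urban trial clients planned over three months. It does not split the clients by provider. With assumed extra injections a per LHV and b per LHW, the urban exposure ratio is (34.2 + a)/(11.4 + b):

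| a | b | LHV:LHW ratio |
|---|---|---|
| 20 | 20 | 1.7 |
| 50 | 50 | 1.4 |
| 100 | 20 | 4.3 |
| 20 | 50 | 0.9 |

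**Effect of the protocol interview threshold.** I simulated 34 LHW clients per urban site (threshold 9) and 10 per rural site (threshold 4), with multinomial allocation to three LHWs and 400,000 runs. The rotation patterns are assumptions.

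| Rotation | Urban LHWs asked (of 15) | Rural LHWs asked (of 15) | Not asked (of 30) | LHW trial doses covered |
|---|---|---|---|---|
| Even | 12.7 | 6.6 | about 11 | 84% |
| 50/30/20 | 9.8 | 6.5 | about 14 | 78% |
| 60/25/15 | 7.7 | 6.1 | about 16 | 75% |

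Part of this needs no simulation. With 10 LHW clients at each rural site, three LHWs cannot all reach four (3 × 4 = 12), so at least 5 of 15 rural LHWs are not asked. If rural sites enrolled more, at 15 LHW clients each with even rotation, 11.9 of 15 rural LHWs would qualify. At r = 1% and even rotation, the threshold moves the expected LHW share from 10.7% to 11.4% at urban sites and from 3.3% to 4.6% at rural sites.

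**The case against.** The strongest objection is that the three-fold gap holds only for trial first doses, and nothing in the plan limits the outcome to those. The timing of the interview suggests that follow-up injections may count too. This stands as a limit on the size and direction of the distortion. It does not rescue the measure: the exposure behind the percentages is then unknown rather than unequal by a known factor.

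The questionnaire is not part of the documents and may state a recall period or the injections covered. That also stands; the point is confined to the protocol and SAP.

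Much of a rate is recoverable from planned output. Table 4 gives n, and SAP section VI reports numbers randomised by cadre, so a reader could form approximate injuries per client if only trial doses count. That is true, but the outcome is defined as the percentage, which is what will be read.

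Expected shares also overstate what one trial would show. With 10 LHVs, one injured provider moves the share by 10 points. Under the same model over all sites, the LHV share would be no higher than the LHW share in about 80% of trials at r = 0.1%, just over a third at 0.5% and 21% at 1%.

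Finally, the outcome carries no test or margin, and the protocol names screening as the primary outcome of interest. This limits the consequence, and it is why the point is a recommended change and not an essential one.

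**Conclusion.** The concern holds. As written, the plan compares cadres on a share of providers without accounting for exposure. If only trial first doses count, equal risk per injection yields an expected LHV share 2.4 to 3 times the LHW share, for assumed risks of 0.1% to 2%, one LHV per site and similar ineligibility by arm. If other injections count, the ratio cannot be determined from the documents. The protocol and SAP contradict each other on which LHWs are interviewed. Under the protocol rule, the LHWs left unasked gave about 16% to 25% of LHW trial first doses, given the rotations assumed and 10 LHW clients per rural site. The threshold's effect on the needle-stick share is modest under even rotation. The powered screening comparison is unaffected.

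**What to change.** 1. State the recall window, and ask each provider for the number of needle-stick injuries during trial injections in that window. List injuries from follow-up and other injections separately.
2. Report injuries per trial injection by cadre beside the provider n (%), with the denominator counted from the injection checklists already planned. Give an exact 95% interval labelled as descriptive and as ignoring clustering within provider, or a cluster-aware interval if there are enough events.
3. Reconcile the protocol's interview rule with SAP section V.B so that the needle-stick and log items are asked of all participating LHWs, as the SAP states. The nine- and four-client thresholds can remain for the questions on perspectives.

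The cost is wording in both documents, one clarified question, and roughly 5 to 16 more short interviews than under the protocol rule (none beyond the SAP rule). Design, sample size and the screening test do not change.

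The drawback is imprecision. With no injuries in 171 injections, the upper limit is 1 − 0.025^(1/171) = 2.1% if injections are independent. Replacing 171 by 171/(1 + (m − 1)ICC), with m = 34.2 or 11.4 and an assumed within-provider correlation (ICC) of 0.01 to 0.05, gives about 2.8% to 5.6% for urban LHVs and 2.4% to 3.2% for urban LHWs.
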